9.4 Pregnancy Reporting

If a patient becomes pregnant during the study or within the safety follow-up period defined in the protocol, the Investigator is to stop dosing with study drug(s) immediately and the patient should be withdrawn from the study. Early termination procedures should be implemented at that time.

A pregnancy is not considered to be an adverse event or SAE; however, it must be reported to the ENYO safety designee within 24 hours of knowledge of the event (contact information listed in Section 9.3) The ENYO safety designee will then provide the Investigator/clinical site the Exposure in Utero (EIU) form for completion. The Investigator/clinical site must complete the EIU form and fax/email it back to the ENYO safety designee.

If the female partner of a male patient becomes pregnant while the patient is receiving study drug or within the safety follow-up period defined in the protocol, the Investigator should notify the ENYO safety designee and ENYO safety personnel as described above.

The pregnancy should be followed until the outcome of the pregnancy, whenever possible. Once the outcome of the pregnancy is known, the follow-up EIU form should be faxed/mailed to the ENYO safety designee and ENYO safety personnel. If the outcome of the pregnancy meets the criteria for immediate classification as an SAE (ie, postpartum complication, spontaneous abortion, stillbirth, neonatal death, or congenital anomaly), the Investigator should follow the procedures for reporting an SAE.

9.5 Expedited Reporting

The Sponsor/designee will report all relevant information about suspected unexpected serious adverse reactions (SUSARs) that are fatal or life-threatening as soon as possible to the FDA, applicable competent authorities in all the countries concerned, and to the Central Ethics Committee, and in any case no later than 7 days after knowledge by the Sponsor/designee of such a case. Relevant follow-up information will subsequently be communicated within an additional 8 days.

All other SUSARs will be reported to the FDA, applicable competent authorities concerned, and to the Central Ethics Committee concerned as soon as possible but within a maximum of 15 days of first knowledge by the Sponsor/designee.

The Sponsor/designee will also report any additional expedited safety reports required in accordance with the timelines outlined in country-specific legislation.

The Sponsor/designee will also inform all Investigators as required per local regulation.

The requirements above refer to the requirements relating to an investigational medicinal product.

9.6 Special Situation Reports

Special situation reports include reports of EYP001a or statin overdose, misuse, abuse, and medication error.

- **Overdose:** Refers to the administration of a quantity of EYP001a or statin given per administration or cumulatively (accidentally or intentionally), which is above the maximum recommended dose according to the protocol. Clinical judgement should always be applied. In cases of a discrepancy in the drug accountability, overdose will be established only when it is clear that the patient has taken additional dose(s) or the Investigator has reason to suspect that the patient has taken additional dose(s).
- **Misuse:** Refers to situations where EYP001a or statin is intentionally and inappropriately used in a way that is not in accordance with the protocol instructions or local prescribing information and may be accompanied by harmful physical and/or psychological effects.
- **Abuse:** Is persistent or sporadic, intentional excessive use of EYP001a or statin, which is accompanied by harmful physical or psychological effects.
- **Medication error:** Is any unintentional error in the prescribing, dispensing, or administration of EYP001a or statin by a healthcare professional, patient, or consumer, respectively. The administration or consumption of the unassigned treatment and administration of an expired product are always reportable as medication errors. Cases of patients missing doses of study drug are not considered reportable as medication error.

All special situation events as described above must be documented and captured in the eCRF. All adverse events associated with these special situation reports should be reported as adverse events or SAEs as well as recorded on the adverse event eCRF and/or the SAE report form. Details of the signs and symptoms, clinical management, and outcome should be provided, when available.

9.7 Medical History

Medical history, including information on prior and concomitant medication, will be collected for all patients at screening. Data from previous liver biopsies are not a prerequisite for enrollment but should be collected if available in the patient's medical record.

9.8 Clinical Laboratory Evaluations

Clinical safety laboratory parameters will be measured or calculated at study visits specified in [Appendix A](#). Profiles for hematology, coagulation, serum chemistry, lipid and metabolic parameters, and urinalysis will be evaluated from samples collected after ≥ 6 hours of fasting (nothing by mouth except water). Further analysis of urine sediment or urine microscopy will be performed when there are any abnormalities on any of the following 3 dipstick results: leukocyte esterase, blood, or nitrite, and if judged clinically significant by the Investigator. See [Appendix B](#) for a complete list of laboratory analytes.

For women of childbearing potential, a serum hCG test will be performed at screening and the EOS and ET Visits. Urine hCG testing will be performed at visits specified in Appendix A. If a urine hCG test is positive, a serum hCG test will be performed.

Follicle-stimulating hormone level will be measured at screening to confirm postmenopausal state in women ≤ 55 years of age.

Anti-HBV, anti-HCV, and anti-HIV will be assessed at screening, and HCV RNA will be reflexively tested. Samples will be collected for central laboratory analysis except if viral serology data is already available in patient's medical history/records and obtained within 90 days prior to screening.

Plasma from blood samples obtained at screening and at study visits specified in Appendix A, including EOS and ET Visits, will be stored for protocol-related safety testing or exploratory analyses.

Blood sampling procedures, including information on blood volume, collection tubes, sample processing, storage, and shipping are provided in the Laboratory Manual.

The safety of statin coadministration will be assessed at study visits specified in Appendix A by monitoring CK levels.

Technical details on laboratory parameters (methods and commercial kit[s]) will be specified in the Laboratory Manual.

Additional laboratory testing may be required in response to adverse events and laboratory findings as described in the Clinical Safety Monitoring Plan ([Appendix E](#)). Laboratory abnormalities should be reported as an adverse event if any of the following is applicable:

- If an intervention is required as a result of the abnormality (such as a re-test being performed more than 1 time)
- If action taken with the study drug is required as a result of the abnormality

9.9 Vital Signs and Anthropometrics

Vital signs (systolic and diastolic blood pressure, heart rate, respiratory rate, and body temperature) and anthropometrics (height, body weight, BMI, waist circumference, hip circumference [Part B only], WHR [Part B only], and WHtR [Part B only]) will be assessed as specified in [Appendix A](#).

Blood pressure will be measured using a standardized process:

- Clinical site staff will assess blood pressure with the patient in the sitting position after 5 minutes of rest and before any blood draws.
- Clinical site staff will use a mercury sphygmomanometer or automatic blood pressure device with an appropriately sized cuff with the bladder centered over the brachial artery.
- Clinical site staff will record the arm used for the measurement and use the same arm throughout the study.
- Clinical site staff will measure and record the blood pressure.

Blood pressure will be recorded to the nearest 2 mmHg mark on the manometer or to the nearest whole number on an automatic device. A blood pressure reading will be repeated 1 to 2 minutes later, and the second reading will also be recorded to the nearest 2 mmHg mark.

Waist circumference will be measured using a standardized process:

- Measure the waist circumference at the end of several consecutive natural breaths, at a level parallel to the floor, midpoint between the top of the iliac crest and the lower margin of the last palpable rib in the mid axillary line. The tape should be placed around the abdomen at the level of this midway point and a reading taken when the tape is snug but does not compress the skin.¹⁹

Hip circumference will be measured using a standardized process:

- Measure the hip circumference at a level parallel to the floor, at the largest circumference of the buttocks. The tape should be placed around the hips and a reading taken when the tape is snug but does not compress the skin.

9.10 Electrocardiograms

Single 12-lead ECGs will be performed at screening; on Days 7 (Part A only), 14, 21 (Part A only), 28, 56, and 84; and at the EOS and ET Visits after the patient has been resting in the supine position for at least 10 minutes. The ECG will include 12 standard leads and will be recorded at a paper speed of 25 mm/sec. QT interval corrected for heart rate using Fridericia's formula will be measured.

In case of evident bad quality of the tracing (eg, muscle tremor), the ECG will be repeated. See [Appendix A](#).

9.11 Physical Examinations

A complete physical examination (including general appearance; eyes, ears, nose, and throat; head and neck; chest and lungs; cardiovascular; abdomen; musculoskeletal; lymphatic; dermatological; neurological systems; mental status; and extremities) will be performed at screening. Brief, symptom-directed physical examinations will be performed in Part A at each study visit after screening and in Part B on Days 1, 14, 28, 56, and 84; and at the EOS and ET Visits. See [Appendix A](#).

9.12 Pruritus Assessments

In Part A, the pruritus visual analog scale and 5-D questionnaire (degree, duration, direction, disability, and distribution) itch scale will be assessed at each study visit after screening. See [Appendix A](#).

In Part B, pruritus will be reported as any other adverse event. If a patient reports pruritus, the visual analog scale and the 5-D questionnaire (degree, duration, direction, disability, and distribution) itch scale will be administered.

9.12.1 Pruritus Management – Guidance to Investigators

Mostly mild to moderate pruritus has been observed in clinical trials with EYP001a and has also been reported with other FXR agonists and in patients with NASH. Pruritus is also part of the natural disease symptomatology of NASH and independent of any pharmacological treatment. Tolerance to pruritus may develop over continuous, uninterrupted dosing or after a short (few days) interruption of EYP001a (empirical observations).

The following 3-level therapeutic approach to pruritus should be applied:

1. Topical non-pharmacological or over-the-counter interventions to improve pruritus may be tried and can be advised to patients. These include application of moisturizers, cooling agents, and antihistamines; or taking cool showers/showering in the morning, using clear/gentle soaps and laundry detergents, application of cold packs or fabric strips soaked in cold water, avoidance of wool or other irritating fabrics, and wearing loose-fitting clothing.
2. In the case of no improvement of pruritus, a drug holiday of 2 days to a maximum of 5 days may be implemented.
3. In the case pruritus prevails and requires systemic oral pharmacological treatment, it is encouraged to seek advice from the Medical Monitor. Recommended possible comedications for pruritus are: naltrexone (25 to 50 mg/day orally [po]), ondansetron (4 to 24 mg/day po), hydroxyzine (25 to 75 mg/day po), sertraline (25 to 75 mg/day po), and gabapentin 300 mg/day po).

Note: Bile acid sequestrants are excluded medications, the concomitant use of naltrexone with gabapentin is disallowed.

9.13 Drug-Induced Liver Injury and Muscle Toxicity Monitoring

Throughout the study, all TEAEs, clinical assessments, and clinical laboratory parameters will be closely monitored against the criteria for drug-induced liver injury and muscle toxicity as detailed in the Clinical Safety Monitoring Plan ([Appendix E](#)). The Clinical Safety Monitoring Plan describes the actions with regard to the study drug that are required upon clinical findings and confirmation of laboratory abnormalities suggestive of muscle toxicity or liver injury of varying degrees as a function of baseline findings.

9.14 Diet and Lifestyle Counseling

Diet and lifestyle counseling will occur as per standard of care. Diet and lifestyle counseling will be performed in Part A at each study visit and in Part B at screening and on Days 1, 14, 28, 56, and 84; and at the EOS and ET Visits. High-level dietary and physical activity guidelines will be provided and documented in the eCRF.

10 STATISTICS

10.1 Analysis Populations

The Intent-to-Treat (ITT) Population includes all patients who are randomized and administered at least 1 dose of study drug. Patients without a Week 12 or end of treatment MRI-PDFF assessment will be imputed as nonresponders unless otherwise specified.

The Safety Population is identical to the ITT Population.

The modified ITT (mITT) Population includes patients from the ITT Population who have valid baseline and Week 12 MRI-PDFF measurements of LFC.

The Per-Protocol Population includes all patients from the mITT Population who finish the 12-week Treatment Period without any major protocol violations. The analysis of LFC as measured by MRI-PDFF will be repeated on the Per-Protocol Population to test the robustness of results.

10.2 Statistical Methods

10.2.1 Analysis of Efficacy

The primary and secondary efficacy analyses are described in the sections below. The efficacy analyses of LFC as measured by MRI-PDFF will be conducted on the ITT Population and repeated on the mITT and Per-Protocol Populations. The analysis of other efficacy variables will be based on the ITT Population.

For efficacy variables, observed data and change and/or percent change from baseline will be summarized using descriptive statistics and graphs per dose group and visit as appropriate.

10.2.1.1 Primary efficacy analysis

The primary efficacy analysis will be performed on the ITT Population. Missing MRI-PDFF values at Week 12 or ET will be imputed based on the missing at random assumption using multiple imputation.

The primary efficacy analysis will be performed on the change in LFC as measured by MRI-PDFF from baseline to Week 12 or ET using an analysis of covariance (ANCOVA) model with baseline fat fraction as a covariate and treatment, use of statin comedication at screening (stratification factor: use of statin [yes, no]), and T2DM status (yes, no) in Part A, and by statin use (yes, no) and LFC at screening (stratification factor with 3 categories: $LFC < 16\%$, $16\% \leq LFC < 22\%$, and $22\% \leq LFC$) in Part B, as factors. Pairwise treatment comparisons between each EYP001a dose and placebo will be conducted from the ANCOVA model with least-square means, standard errors, 95% confidence intervals, and p-values being presented. To adjust the 3 tests (each EYP001a dose and placebo) for multiplicity in order to control the family-wise type I error at 0.025 one-sided, the Bonferroni method will be used.

The primary efficacy results will subsequently be analyzed by adding LSMs and CAP values at enrollment as additional factors.

10.2.1.2 Sensitivity analysis

Sensitivity analyses will be conducted by repeating the primary efficacy analysis based on:

- The ITT Population with missing MRI-PDFF values at Week 12 or ET imputed using the multiple imputation with tipping point method based on the missing not at random assumption
- The mITT Population

10.2.1.3 Secondary efficacy analysis

The statistical analysis of secondary efficacy variables based on change from baseline to Week 12 will be conducted with a similar ANCOVA model, while secondary efficacy variables measured at multiple timepoints will be analyzed by mixed effect model repeated measures model.

The responder (categorical) variables will be analyzed by a Cochran-Mantel-Haenszel test, stratified by statin comedication use and T2DM status at screening in Part A and statin comedication and LFC at screening in Part B. The analysis of the responder variables will be repeated using logistic regression models, adjusting for treatment, statin comedication at screening, and T2DM status at screening. Patients without a Week 12 or end of treatment MRI-PDFF assessment will be imputed as nonresponders. All secondary efficacy variables will be summarized using descriptive statistics.

10.2.1.4 Validation of nonalcoholic steatohepatitis disease model

The anticipated EYP001-202 efficacy results will serve as validation of an in silico NASH disease model, which was built based on public and expert knowledge and combined with the Phase 1 PK and PD EYP001 results.¹⁵ The model integrates 309 liver FXR-related biological variables and 1320 parameters and explores the effect of different EYP001 treatment regimens on NASH-relevant efficacy endpoints in a virtual population. Iterations of the model will support future explorations of development strategies with different EYP001 Phase 2 and 3 study designs.

10.2.2 Pharmacodynamic Analysis

Pharmacodynamic parameters, observed data, and change and/or percent change from baseline will be summarized using descriptive statistics and graphs per dose group and visit, as appropriate.

10.2.3 Pharmacokinetic Analysis

Plasma concentrations of EYP001a will be listed for all patients with available EYP001a plasma concentrations in treatment groups that include EYP001a or placebo. All concentrations below the limit of quantification will be labeled as such in the concentration data listings and will be treated as 0 in the summary statistics.

Listings of individual patient plasma concentrations and actual blood sampling times and graphs of concentration versus time will be prepared by dose. Plasma concentrations will be summarized by and compared among different doses using descriptive statistics.

10.2.4 Analysis of Safety

Baseline for physical examinations, all vital signs, 12-lead ECG measurements, pruritus questionnaire (Part A only), and clinical laboratory assessments will be defined as the last evaluation done before the first administration of study drug in each dose group on Day 1.

Safety variables will be tabulated and presented for the Safety Population.

10.2.4.1 Adverse events

The original terms used in the eCRF by Investigators to identify adverse events will be coded using the current version of the Medical Dictionary for Regulatory Activities (MedDRA). All adverse events will be assessed and reported using the National Cancer Institute CTCAE Version 5.0 grading system. A TEAE is defined as a new or worsening adverse event after the first dose of study drug. The percentage of patients with TEAEs will be summarized for each dose group by system organ class and preferred term. The study drug-related TEAEs and SAEs will be summarized in the same fashion. The TEAEs will also be summarized by system organ class, preferred term, and maximum severity. All SAEs and TEAEs leading to early discontinuation will be listed.

The safety of EYP001a with statin coadministration will be assessed based on the difference in frequency of TEAEs between treatment groups.

10.2.4.2 Laboratory values

The clinical laboratory analytes at each visit and change from baseline will be summarized descriptively. Abnormalities based on predefined normal ranges will be tabulated by dose group showing patient counts and percentages. A listing of patients with any laboratory results outside the reference ranges will be provided if appropriate.

10.2.4.3 Vital signs, anthropometrics, and electrocardiograms

Vital signs, anthropometrics, and ECGs at each visit assessed and change from baseline will be summarized descriptively.

10.2.4.4 Prior and concomitant medications

Prior and concomitant medications will be coded with the World Health Organization (WHO) Drug Dictionary. A prior medication is defined as any medication taken by the patient before the first dose of study drug. A concomitant medication is defined as any medication taken by the patient at the same time or after the first dose of study drug. Number and frequency of patients taking prior and concomitant medications will be tabulated and listed.

10.2.5 Demographic and Baseline Characteristics

For all patients who receive at least 1 dose of study drug, descriptive statistics (mean, standard deviation, median, minimum, and maximum) will be performed for age, gender, race and ethnicity, BMI, waist circumference, WHR (Part B only), WHtR (Part B only), body weight, and height.

10.2.6 Interim Analysis

All available unblinded preliminary safety, PK, and PD results will be comprehensively reviewed during 2 interim analysis timepoints:

- The first interim analysis will be performed at the end of the Safety Run-in Period, after the last of the 24 patients randomized in Part A has completed Day 28 (Week 4). It is anticipated that at the time of the first interim analysis, approximately 10 patients will have completed Day 84 (Week 12) of Part A.
- A second interim analysis will be performed when 50% of patients in Part B have completed Day 56 (Week 8).

The interim analyses will be performed on all available primary and secondary endpoints according to the DSMC charter. The conclusions and recommendations of the DSMC will be shared blindly with the Sponsor and clinical sites.

10.2.7 Data and Safety Monitoring Committee

An external, independent DSMC will review all available unblinded preliminary safety, PK, and PD results when any stopping rules are met and in accordance with the interim analysis timepoints described in Section 10.2.6. In Part B, the DSMC will be promptly notified for further review if any patients experience ALT, AST, or bilirubin elevations 2 \times above baseline values.

The interim analyses will be performed on all available primary and secondary endpoints according to the DSMC charter, which describes the overall guidelines, composition, roles, and responsibilities of the independent DSMC for this study, including the selection of DSMC members, timing of meetings, methods of providing information to and from the DSMC, frequency and format of meetings, data analysis recommendations, and DSMC relationships with other parties participating in the conduct of this study. Patient accrual will continue throughout the period of DSMC review. The DSMC will advise on the accrual of the remaining patients per protocol or on any amendments that are necessary for safety reasons.

10.2.8 Sample Size Determination

The sample size of 114 randomized patients (n = 24 patients in Part A and n = 90 in Part B [n = 30 patients per treatment group]) is based on the efficacy endpoint: absolute change in LFC as measured by MRI-PDFF from baseline to Week 12, assuming that the treatment difference between each active treatment group with placebo is at least 5.1% with a common standard deviation of 5.8%.

With a 2-sample Z-test with the power of 0.8 and an overall family-wise 1-sided alpha of 0.025 (or each active versus placebo alpha = 0.0125 after Bonferroni adjustment), 26 patients per treatment group will be needed to complete the Week 12 Visit. With the consideration of an approximately 13% dropout rate before Week 12, 30 patients will be randomized per treatment group in Part B.

A Lan-DeMets alpha spending function will be used for this group sequential design. Nonbinding O'Brien-Fleming efficacy boundaries and futility boundaries will be calculated using EAST 6.4 software. The efficacy and futility boundaries are described in [Table 6](#).

At the time of the interim analysis, if the test-statistic is equal to or less than the futility boundary, the Sponsor can decide to stop the study due to lack of efficacy.

Table 6. Efficacy and Futility Boundaries for Part B

Look	Week 8 Number of Patients	Week 12 Number of Patients	Information Fraction	Cumulative Alpha Spent	Cumulative Beta Spent	Z Efficacy Boundary	Z Futility Boundary	p-value Efficacy Boundary	p-value Futility Boundary
#1 (interim analysis)	45	23	0.25	<0.0001	0.0113	-4.7604	0.6966	<0.0001	0.7570
#2 (final analysis)	90		1	0.0125	0.1962	-2.2414	-2.2414	0.0125	0.0125

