5.3 Randomization and Blinding

This study follows a randomized, double-blind, placebo-controlled design. Patients in Part A will be randomized via the Interactive Response Technology (IRT) system to 1 of 4 parallel treatment groups on Day 1 in a 1:1:1:1 ratio. However, prerandomization will occur within the IRT system at least 7 days prior to randomization. Patients in Part B will be randomized via the IRT system to 1 of 3 parallel treatment groups on Day 1 in a 1:1:1 ratio. Prerandomization is not applicable in Part B.

Both EYP001a and placebo will be provided as tablets for oral administration and will be identical in appearance.

Prerandomization/randomization information will be concealed from the Investigators and the patients until the end of the study, with the exception of an emergency situation involving a patient that required unblinding of the treatment assignment.

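### Table 6's interim boundaries were computed for 25 patients per arm at information fraction 0.26, not for the stated 26 per arm and 0.25, and the fraction's denominator is not stated

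*Protocol*

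**What the plan says.** Protocol 10.2.8 assumes that the difference of each active arm from placebo "is at least 5.1% with a common standard deviation of 5.8" percentage points. It sizes the trial "With a 2-sample Z-test with the power of 0.8 and an overall family-wise 1-sided alpha of 0.025", that is, "each active versus placebo alpha = 0.0125 after Bonferroni adjustment", and concludes that "26 patients per treatment group will be needed to complete the Week 12 Visit". It then inflates: "With the consideration of an approximately 13% dropout rate before Week 12, 30 patients will be randomized per treatment group in Part B". Allocation in Part B is 1:1:1 (Protocol 5.3).

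On monitoring, the same section states: "A Lan-DeMets alpha spending function will be used for this group sequential design". The boundaries are of nonbinding O'Brien-Fleming type, and the section says that "efficacy boundaries and futility boundaries will be calculated using EAST 6.4 software". Table 6 gives:

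- Interim look: 45 patients at Week 8, 23 at Week 12, information fraction 0.25, cumulative beta 0.0113, Z efficacy -4.7604, Z futility 0.6966 (p 0.7570).
- Final look: 90 patients (in the Week 8 column), fraction 1, cumulative alpha 0.0125, cumulative beta 0.1962, Z -2.2414 for both boundaries.

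The text lets the sponsor stop for lack of efficacy when the statistic is at or below the futility boundary. SAP 2.2.4 repeats the sample size without boundaries. SAP 4.1 refers to a separate Interim Analysis Plan and says that the Part B interim was completed in February 2021.

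**The concern.** With a Lan-DeMets spending function of this type, the first efficacy boundary depends only on alpha and the information fraction. A boundary printed to four decimals can therefore be checked directly against the fraction beside it, and here the two do not match. The futility boundary also depends on the sample size, and it does not match the planned 26 per arm.

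In addition, 0.25 has no stated denominator. The table sets 23 patients with Week 12 data beside a final count of 90, which is the number randomized, while the power calculation rests on 3 × 26 = 78 completers.

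At stake is a decision threshold: the futility line is what allows the sponsor to stop Part B for lack of efficacy. In the two documents, Table 6 is the only specification of that line.

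**Working it through.** **Inputs** (all Protocol 10.2.8): difference 5.1, SD 5.8, one-sided alpha 0.0125 per comparison, 26 completers per arm, and the Table 6 entries.

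**Sample size.** n = 2 × [(2.2414 + 0.8416) × 5.8/5.1]² = 24.59, so the stated Z-test gives 25 per arm. A t-test gives 26 (power 0.802). Dropout: 26/(1 - 0.13) = 29.9, so 30.

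**Formulas.**
- Alpha spent at fraction t: 2 × [1 - Φ(z/√t)], with z = 2.4977, the upper 0.00625 point. The efficacy Z is the normal quantile of the amount spent.
- Beta spent: the same function, with total beta in place of alpha.
- Futility Z = z(beta spent) - θ√t, where θ = (5.1/5.8) × √(n/2) and negative Z favours the drug.
- Total beta is either held at the printed 0.1962 or solved so that it equals one minus the power of the two-look design with the futility rule applied.

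**Reproducing the table.** Solving for the printed -4.7604 gives t = 0.2600: 2.4977/√0.26 = 4.898, alpha spent 9.66 × 10⁻⁷, Z = -4.760. With 25 per arm, θ = 0.8793 × √12.5 = 3.109 and θ√0.26 = 1.585. The solved total beta is 0.1962, with 0.0112 to 0.0113 spent at look 1, so futility Z = 2.282 - 1.585 = 0.697. Every printed look 1 and look 2 figure is recovered. Neighbouring sample sizes fail: at t = 0.26 the solved total beta is 0.1874 for 25.5 per arm and 0.1790 for 26.

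**Using the plan's 26 per arm** (θ = 0.8793 × √13 = 3.170):

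| Fraction | Efficacy Z | Futility Z, beta 0.1962 | Futility Z, beta solved | Chance of Z at or above the line, no effect |
|---|---|---|---|---|
| 0.25 (as printed) | -4.860 | 0.75 | 0.86 (beta 0.179) | 23% to 19% |
| 23/90 = 0.256 | -4.804 | 0.70 | 0.81 (beta 0.179) | 24% to 21% |
| 23/78 = 0.295 | -4.453 | 0.39 | 0.49 (beta 0.1805) | 35% to 31% |
| Table 6 | -4.7604 | 0.6966 | | 24% |

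The last column is 1 - Φ(futility Z), for example 1 - Φ(0.6966) = 0.243.

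**Direction of the rule.** In Table 6 negative Z favours the drug, since efficacy is declared at -4.7604 and -2.2414. Futility should then mean Z at or above 0.6966. The text says at or below. Read literally, that condition holds with probability Φ(0.6966) = 76% under no effect and Φ(0.6966 + 1.585) = 99% under the planned effect.

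**The case against.** A reader might infer from the two mismatches that the printed futility line is too far out and will fail to stop an ineffective dose. The documents do not support that. Correcting only the two mismatches, to 0.25 and 26 per arm, moves the line outward, to 0.75 to 0.86. With the 90 shown in Table 6 as denominator, 0.6966 is about right or slightly too near zero.

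The line is too far out only if information is 23 of 78 completers, and the protocol never says so. The 23 may be no forecast of scans at all but half of 45 rounded up (22.5). In that case the numerator is on the randomized scale, and applying the 13% dropout to it as well gives about 20/78 = 0.256. Scans from early termination visits, taken after at least 4 weeks on drug, also enter the primary endpoint (Protocol 10.2.1.1; SAP 3.4.1.1) and could bring the final count above 78. Against that, such scans may also be available at the interim. Imputed values add essentially no information either, because the imputation model in SAP 3.4.1.1 holds only treatment, statin use and baseline LFC for Part B. The denominator is therefore open, and 0.295 should not be treated as the true fraction.

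The gaps may also have innocent origins: 25 is the result of the stated Z-test, and a quarter of 50 patients per comparison is 12.5, which rounds up to 13 and gives 13/50 = 0.26. That is an inference. It would explain the figures but not reconcile them with the text.

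Finally, Lan-DeMets spending is meant to be recalculated at the information observed, the boundaries are nonbinding, the sponsor only may stop, and the Interim Analysis Plan, which is not among these documents, may hold corrected values. All of this stands and keeps the point minor.

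**Conclusion.** Table 6 is inconsistent with its own stated inputs. The efficacy boundary alone settles the fraction: -4.7604 belongs to 0.26, and 0.25 would give -4.860, whatever the sample size. The futility boundary and total beta then identify 25 per arm rather than 26.

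The practical size depends on a denominator that the protocol leaves out. With 26 per arm, the futility Z ranges from 0.39 (23/78, beta 0.1962) to 0.86 (0.25, beta solved), around the printed 0.6966. The chance of crossing with no effect ranges correspondingly from 35% to 19%, against 24% for the printed line. No direction of error can be asserted without the denominator. Type I error is essentially unaffected, because futility is nonbinding and the alpha spent at the interim is of the order of 10⁻⁶.

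These results assume O'Brien-Fleming-type spending for both alpha and beta, which the exact reproduction supports. The crossing probabilities assume that Z at or above the line counts as futility, which follows from the table's signs but contradicts the text. That contradiction needs correcting together with the numbers. The point is minor in severity.

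**What to change.** 1. Define the information fraction on one basis: patients with Week 12 or early termination MRI-PDFF at the interim, over the number expected with such a scan at the final analysis.
2. Recompute Table 6 from 26 per arm at the matching fraction, with the total beta that this design implies, and print fraction, counts and boundaries that agree.
3. State that the boundaries are recomputed from the actual number of scans at the interim.
4. Reconcile the text's at-or-below futility condition with the table, where negative Z favours the drug.
5. Because SAP 4.1 reports the Part B interim as completed, record in the SAP or study report which fraction, boundaries and direction were applied.

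Cost: one run of the boundary software, one corrected table and a few sentences. No change to sample size or conduct follows from it.
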